At the in-person screening visit, a civilian research staff member will review the consent document with the study candidate, allow time for the individual to read the document and ask any questions. If the individual wishes to review the consent with their family or physician, they will be allowed the time to do so and will be re-scheduled to complete the screening visit once they are ready to sign the consent form. If the individual wants to volunteer, they will be asked to sign the consent document and the HIPAA Authorization document. Another civilian member of the research team will witness the consent. Once informed consent is obtained, the research staff will confirm eligibility by collecting demographic information, physical measurements (i.e. height, weight), an array of screening visit questionnaires (see Section 3.6.2), and contact information. A 1-2 week run-in will be explained (see section 3.6.2) and the participant will receive additional instructions that must be completed in order to be included in the study (i.e. obtain military medical clearance, participate in 1 week of dietary and physical activity self-monitoring). The screening visit will take approximately 60 minutes.

The participant will return for the baseline visit in approximately 1-2 weeks at the HAWC. At this visit, run-in material will be reviewed for completeness, physical measurements will be taken (i.e. weight, abdominal circumference, blood pressure and heart rate), and the participant will be randomly placed into one of the two treatment groups. The abdominal circumference measurement will be assessed using the criteria stated in AFI 36-2905, "Fitness Program," Section 7. At this time, research staff will also inquire into current adverse events, such as physical injuries, illnesses or hospitalizations. Fifty percent of participants will be randomly assigned, using a computerized block design unique to the Filemaker v12 relational database application, to the more structured counselor-initiated weight loss intervention and 50% to the self-paced weight loss intervention. If the participant is assigned to the counselor-initiated group, he/she will be oriented to the group and study website, provided lesson materials, exercise guidelines, an electronic body scale, meal replacements, and measuring cups and spoons. If the participant is assigned to

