the self-paced group, he/she will be oriented to the group and study website, and will be provided exercise guidelines, an electronic body scale, measuring cups and spoons, and a Fit Blue t-shirt. The Body Trace electronic body scales will be issued to the subject on a hand receipt and will be returned at the completion of the study. This baseline visit will take approximately 60 minutes. For the Look Ahead Pilot Study (FWH20130053H), the AF/SG Legal Office made the determination that meal replacements, weight scale and measuring cups/spoons were integral to the study and should not be considered as gifts to the research subjects. It was also determined the use of meal replacements was not in violation of regulations governing a BAS food allowance for active duty members. The gift of a T-shirt was within the monetary allowance for gifts to military members and did not require any special approval through the Hospital Commander. The WHASC IRB agreed these items did not increase the risk to the subjects nor were they unfair inducements or coercive.

The participants will spend the next 12 months involved in study interventions, diet and exercise selfmonitoring, daily weighing, and may also include telephone counseling sessions. A detailed description of intervention procedures is listed in section 3.6.1.

The next in-person session will occur 4 months after randomization. This is the 4-month follow-up visit. At this visit, physical measurements will be collected (i.e. height, weight, abdominal circumference, blood pressure and heart rate) and participants will complete various questionnaires. A Quality of Life questionnaire will also be administered by study personnel. A business card magnet will be given to them as a reminder of the 12 month follow up visit.

The final in-person session will occur 12 months after randomization. At this visit, physical measurements will be collected (i.e. height, weight, abdominal circumference, blood pressure and heart rate), participants will complete various questionnaires and a program evaluation. A Quality of Life questionnaire will also be administered by study personnel. A template EPR/OPR bullet will be given to them upon completion of the last data collection visit.

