- Self-Monitoring: Because self-monitoring has been shown to be significantly associated with weight loss, participants will be asked to monitor food intake, physical activity and weight daily. Participants will be asked to use the Lose It app/website which, with their permission, the study staff will be able to access in order to retrieve their food and physical activity information. Monitoring of weight will be facilitated by the use of the BodyTrace e-scale. Each participant will be provided a scale which will upload their daily weight to a secure website (HIPPA compliant) which our study staff can access. Participants will receive feedback on self-monitoring through email.
- Dietary goals: Dietary goals will be based on weight and will be personalized based on participants' weight-loss progress and goals.
- Meal Replacements: Meal replacements will be provided to participants in the counselor-initiated group at no cost. Vouchers for meal replacement products will be given to participants to use at local grocery stores. Participants will be encouraged to replace 2 meals (typically breakfast and lunch) and a snack with meal replacements. Participants may elect not to use meal replacements. If so, detailed meal plans (for all meals) using common foods that are designed to control portion size and calories will be provided to the participant.
- Physical Activity Goals: Taking into account the amount of physical activity for each participant at the beginning of the program, participants will be asked to gradually increase their cardiorespiratory (aerobic) exercise > 5 days per week at a moderate to vigorous intensity level for 40 to 60 minutes per day (each bout lasting a minimum of 10 minutes), until they reach a total of 225-250 minutes per week. Upon reaching the physical activity goal of 225-250 minutes per week, they will be asked to maintain this level of physical activity.
- Toolbox: The Toolbox includes additional treatment options for those who wish to take advantage of them. Items may include: food scales, exercise videos, cookbooks, etc. These items may be checked out from Fit Blue staff members, but must be returned prior to the completion of the study.

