- Physical Activity Goals: Taking into account the amount of physical activity for each participant at the beginning of the program, participants will be asked to gradually increase their cardiorespiratory (aerobic) exercise > 5 days per week at a moderate to vigorous intensity level (each bout lasting a minimum of 10 minutes), until they reach a total of 225-250 minutes per week. Upon reaching the physical activity goal of 225-250 minutes per week, they will be encouraged to maintain this level of physical activity.

3.6.2. Data Collection and Processing:

Pre-screening (via phone):

- Description of the research project
- Determine eligibility
- Collect name and contact number with oral approval by potential participants
- Schedule in-person screening visit
- Screening visit (in-person):
 - Confirm eligibility
 - Measure weight and height
 - Obtain informed consent
 - Collect demographic information
 - Collect contact information
 - Quality of Life questionnaire (administered by study personnel)
 - Complete brief dietary, physical activity, and weight-related attitudes and behavior questionnaires
 - Explain the 1 to 2 week run-in: The run-in consists of two components: one week of dietary and physical activity self-monitoring and obtaining a letter from their AF healthcare provider approving participation in the intervention (by visiting their healthcare provider or utilizing MiCare, the Air Force's secure patient portal)
 - Participants will use the Lose It! web/mobile based app to collect their diet and physical activity information. Participants will be asked to provide a valid personal e-mail address to access and use Lose It!. If they do not have one or do not wish to use their current personal email address, study staff will assist them in creating a new account for the purpose of

accessing Lose It!. Materials and instruction on using Lose It! will be provided to the participants.

Baseline visit (in-person, 1-2 weeks after screening visit):

- Determine whether run-in requirements were completed
- Measure weight, abdominal circumference, resting blood pressure and resting heart rate
- Randomize participant: If all of the above are completed satisfactorily, participants will be randomized to either the Counselor-initiated intervention group or the Self-paced intervention group.
- Orientation to group assignment and study website

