 - We will ask the participant if they might be willing to receive follow-up information forms while deployed. The follow-up information would be sent via the participants' preferred email address one time, if the participant agrees.
 - If the participant agrees to receive an email with attached follow-up forms while deployed, an email will be sent immediately reminding them of this approval.
 - If the participant does not want to receive a follow-up email, no email will be sent.
 - Communication frequency if participant agrees to continue participation in the study while deployed:
 - One email only during deployment with attached follow-up assessment forms.
 - Measures:
 - Weight
 - Questionnaires if interested and able
 - Will not obtain abdominal circumference, blood pressure, and heart rate
 - Method of data collection: email
 - Deployment email address will NOT be used, unless specifically requested by participant
 - Will give an additional 2 week window on either side of the typical 4-week data collection window
 - For those already deployed, an email will be sent giving options for treatment engagement and asking for interest/ability to provide follow-up information

• PCS/RETIRED: Protocol for 4 month and 12 month data collection

- If retired and in the San Antonio area:
 - Communication frequency:
 - Usual protocol
 - Measures: full data collection
 - Weight and height (on the Body Trace scale and another scale, if not in-person)
 - Questionnaires if interested
 - Abdominal circumference, blood pressure, and heart rate
 - Method of data collection: in-person (if possible); if not- phone, email, or mail (in this order)
- o If not in the San Antonio area:
 - Communication frequency:
 - Usual protocol
 - Measures:
 - Weight (on the Body Trace scale and another scale)
 - Questionnaires
 - Will not obtain abdominal circumference, blood pressure, and heart rate
 - Method of data collection: phone, email, or mail (in this order)
- Will give an additional 2 week window on either side of the typical 4-week window to attempt in-person data collection

• EXTENDED TDY: Protocol for 4 month and 12 month data collection

- If in-person data collection is not possible:
 - Communication frequency:

- Usual protocol
- Measures:
 - Weight (on the Body Trace scale and another scale)
 - Questionnaire
 - Will not obtain abdominal circumference, blood pressure, and heart rate
- Method of data collection: phone, email, or mail (in this order)

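### Do off-site follow-up weights, with no stated rule for which reading counts, threaten the comparison of percentage weight loss?

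*Combined protocol and SAP*

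**What the plan says.** Follow-up visits at 4 and 12 months are in person at the base Health and Wellness Center (Sections 3.6 and 3.6.3), where staff measure weight. Section 3.6.2 adds procedures for participants who become unavailable:

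- **Moved station or retired outside the area, and extended temporary duty:** "Weight (on the Body Trace scale and another scale", with "Method of data collection: phone, email, or mail (in this order". Retirees in the area who cannot attend also use two scales.
- **Deployed:** weight is listed with no scale named, and contact is limited: "One email only during deployment with attached follow-up assessment forms".

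In both arms the home scale will "upload their daily weight to a secure website (HIPPA compliant) which our study staff can access" (Section 3.6.1). The scales "will be issued to the subject on a hand receipt and will be returned at the completion of the study" (Section 3.6). Participants learn their arm at the baseline visit ("Orientation to group assignment and study website", Section 3.6.2).

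Section 6.1 defines the primary outcome as percentage weight loss. Section 6.3 specifies intention to treat, with baseline weight as a covariate. Neither ranks the sources of a follow-up weight or mentions a check by mode of measurement.

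Staff weigh participants twice before treatment: at screening ("collecting demographic information, physical measurements (i.e. height, weight", Section 3.6) and at the baseline visit one to two weeks later ("Measure weight, abdominal circumference, resting blood pressure and resting heart rate", Section 3.6.2).

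**The concern.** One off-site visit can yield two or three candidate weights: the study-scale reading as uploaded, the same reading as passed on by the participant, and the second-scale reading. Some of these pass through a person who knows their assignment and may want to show success. The arms also differ in staff contact, since calls and feedback are initiated by the counselor in one and come on request in the other. Unequal reporting is therefore conceivable.

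With no written precedence, an analyst could in principle choose the number after seeing the data. If many weights were relayed, and misreported differently by arm, the arm difference would carry a bias that intention to treat does not remove. The existence of two pre-treatment weights seems to add a second loose end, because Section 6.3 does not tie the covariate to a visit.

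**Working it through.** **Inputs from the documents.** 124 participants per arm (Section 6.2). No alpha, power, SD, effect size or off-site share is stated, so there is no figure of the plan's own to reproduce.

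**Assumptions.** Two-sided 5% test; 80% power; SD of percentage weight loss 5 to 6 points; mean weight 90 kg; off-site share *p* of 2–10% per arm (0.02 × 124 = 2.5 to 0.10 × 124 = 12.4 people); error *b* of up to 1 kg in a relayed weight.

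**Detectable difference** (two-sample t-test, 124 per arm): 1.79 points at SD 5 and 2.14 points at SD 6. The standard error is SD × √(2/124), which is 0.635 and 0.762.

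**Effect on one person.** 100 × 1/90 = 1.11 percentage points.

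**Bias in the arm difference** = 100 × (p₁b₁ − p₀b₀)/90:

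| p₁ | p₀ | b₁ (kg) | b₀ (kg) | Bias (points) |
|---|---|---|---|---|
| 0.05 | 0.05 | 1 | 1 | 0 |
| 0.05 | 0.10 | 1 | 0.5 | 0 |
| 0.02 | 0.02 | 1 | 0.5 | 0.011 |
| 0.02 | 0.02 | 1 | 0 | 0.022 |
| 0.05 | 0.02 | 1 | 1 | 0.033 |
| 0.05 | 0.05 | 1 | 0 | 0.056 |
| 0.10 | 0.05 | 1 | 0.5 | 0.083 |
| 0.10 | 0.10 | 1 | 0 | 0.111 |
| 0.10 | 0.10 | 1 | −1 | 0.222 |

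The sign reverses if the imbalance reverses. These are scenarios, not bounds. The last row, with errors in opposite directions by arm, is the least plausible.

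**Relative size.** 0.111/1.79 = 6.2% of the detectable difference at SD 5, and 0.111/2.14 = 5.2% at SD 6. The opposite-sign row gives 0.222/1.79 = 12.4% at SD 5.

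**False-positive rate** = Φ(−1.96 − bias/SE) + 1 − Φ(1.96 − bias/SE). At a bias of 0.111 it is 5.35% (SD 5) or 5.24% (SD 6). At 0.056 it is 5.09% or 5.06%. At 0.222 it is 6.4% or 6.0%.

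**What it would take to matter.** With 20% of weights off-site and a between-arm difference in misreporting of 2 percentage points of body weight (1.8 kg at 90 kg), the bias is 0.20 × 2 = 0.40 points and the false-positive rate at SD 5 is 9.7%.

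**How likely that is under the text.** Entry requires at least a year left on station (protocol summary, item 6). Exclusion 14 in Section 3.6.7 removes anyone with an extended absence scheduled in the next 13 months. For those who move, retire or go on temporary duty, Section 3.6.2 adds two weeks on each side of the window to attempt an in-person visit. Off-site weights should therefore come mainly from unplanned absences.

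**Which reading an analyst would take.** The off-site list names the study scale first, and Section 3.6.1 says this scale uploads to staff. The phone, email or mail line covers questionnaires as well as weight, so it does not show that the study-scale value is relayed. The second scale gives a comparison value.

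**Baseline weight.** The protocol keeps the screening visit and the baseline visit distinct. Section 6.0 does use baseline loosely for questionnaires, which are completed at screening. But weight is measured at the visit that bears the name, on the day of randomization, and that is the ordinary reading of the covariate in Section 6.3.

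**The case for a change.** The strongest case for a change is that the off-site share is unknown. Exclusion 14 covers only scheduled absence, and a military population can be moved at short notice, so 10% is not a ceiling; at 20% with a 2-point differential the error rate nearly doubles. Deployed participants are the clearest self-report group, since no scale is named and nothing says the study scale travels with them. A precedence sentence, counts by mode and an in-person-only analysis would use data already held. Dropping 2–10% of weights would raise the detectable difference only from 1.79 to 1.80–1.88 points at SD 5.

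What stands is that the rule is unwritten, the share is not bounded by the text, and such a check would be cheap and informative in a report.

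What does not stand is that the plan as written leads to a wrong result. The damaging scenario needs both a large off-site share and a sizeable difference in misreporting between arms, and the documents suggest neither. For a deployed participant with no upload, ranking the sources would change nothing: the emailed weight would still be the only one. Limiting uploads to the usual four-week window would even conflict with Section 3.6.2, which allows deployed participants two further weeks on each side. Correcting for an offset between scales would not address misreporting by people who know their arm.

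**Conclusion.** No change follows. The plan leaves a detail unwritten; it does not state a rule that misleads. The sensible choice, staff-measured weight first and then the study scale, is what the procedures already point to. Accepting a remote weight from someone who cannot attend is a fair trade against losing that person from an intention-to-treat analysis.

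Under the assumed inputs (2–10% off-site, errors of up to 1 kg in the same direction, 90 kg mean weight, SD 5–6 points), the scenarios worked give a bias of 0 to 0.11 points, 0–6% of the detectable difference, and a false-positive rate of 5.0–5.4%. With errors in opposite directions the bias reaches 0.22 points, about 10–12% of the detectable difference, and the rate 6.0–6.4%. The conclusion rests on off-site weights being uncommon, which the eligibility rules make likely but do not guarantee. The attached Physical Assessment Form and Data Safety Monitoring Plan are not in the documents, so whether the source of each weight is recorded cannot be judged.

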4.4. Assent Process: N/A

4.5. Benefits:

Both study interventions (Counselor-initiated and Self-paced) may produce weight loss. Participants in both intervention groups may increase their knowledge about healthy eating and physical activity. Participants in both intervention groups will receive a complementary Fit Blue T-shirt. The gift of a T-shirt (at baseline visit for self-paced and after a challenge is met for counselor-initiated) is within the monetary allowance for gifts to military members and does not require Hospital Commander approval. However, there is no guarantee or promise of direct benefit for subjects participating in the study.

4.6. Risks:

All study procedures involve only minimal risks to subjects. Since regular exercise will be encouraged, some people may experience some muscle soreness. There are no major risks associated with taking measurements (height, weight, waist circumference, and blood pressure), taking a health history or

collecting questionnaire data. There is, however, the potential risk of loss of confidentiality. Being a part of this study while pregnant may expose the unborn child to significant risks, therefore, pregnant women will be excluded from the study. Women who become pregnant during the course of the study will be withdrawn from the study and referred to their doctor for medical care. Although, we do not anticipate that any study related procedures would increase a participant's risk of suffering from emotional distress or having thoughts of suicide, study procedures are in place so that research staff can respond appropriately if this should occur (see section 4.9 for description of Study Procedures for Distressed Participants).

4.7. Costs: N/A

4.8. Safeguards for Protecting Information

The research consents will be stored in a locked cabinet in a locked room. All research data including patient demographics will be kept in an electronic database, which will be encrypted, double password protected and the access will be restricted. The research data will be de-identified and any links to identifiable data will be destroyed as soon as possible. The research data will not be utilized for further research activity beyond the protocol stipulations without additional IRB approval.

Other study related documents will also be stored in a locked cabinet in a locked room. In addition, this research data will be scanned into an electronic database at UTHSC via a secure connection using Cisco VPN client. The data will be encrypted, double password protected, and access will be restricted. The research database will be managed and maintained at UTHSC. Upon completion of the study protocol, UTHSC will destroy paper forms and links.

4.9. Safeguards for Protecting Subjects:

The principal investigator will be responsible for the protocol safety monitoring. The PI will make study documents readily available for inspection by the local IRB and oversight staff for confirmation of the study data.

Note: A Data Safety Monitoring Plan (DSMP) has been developed for this study (see attached).

Study procedures for distressed participants were developed for research staff to follow in the event that a participant is suffering from emotional distress or having thoughts of suicide.

Several precautions have been taken to both limit the likelihood of participants suffering from a significant psychological event and in the unlikely event that one occurs, we have established appropriate steps for the Counselor to follow in order to get the participant help.

A. PRESCREENING FOR DISTRESS

- 1. All prospective participants are pre-screened by a military medical provider who both screens the participants in person and reviews their electronic medical record. Specifically, all prospective participants are asked whether they have any, "Emotional or psychiatric conditions (depression, schizophrenia)" asked on the *Fit Blue Research Project Medical Clearance Form*.
- 2. Additionally, every prospective participant is asked prior to randomization and every enrolled participant is asked at each follow-up data collection visit the following distress-related questions from the *Health Utilities Index (HUI)*, a quality of life measure, in a Counselor-administered interview:

"33. Would you describe yourself as having felt:"

a) Somewhat unhappy

b) Very unhappy

c) So unhappy that life was not worthwhile?

__ Don't know

___ Refused

"35. How often did you feel fretful, angry, irritable, anxious or depressed?"

a) Rarely

b) Occasionally

c) Often

d) Almost always

__ Don't know

___ Refused

"36. During the past four weeks, did you feel extremely fretful, angry, irritable, anxious or depressed; to the point of needing professional help?"

a) Yes

b) No

__ Don't know Refused

- 3. If any of the following responses are endorsed by the prospective/enrolled participant, the Counselor will (after completing the full Health Utilities Index interview) probe briefly for more information about the circumstances of their distress, including potential suicidality.
 - a. Critical responses include:
 - 1) Item 33 responses b ("very unhappy") and c ("so unhappy that life was not worthwhile")
 - 2) Item 35 responses c ("often") and d ("almost always")
 - 3) Item 36 response a ("yes")
 - b. Counselor will ask whether the participant has a plan to harm his/herself (to act on his/her suicidal thoughts):
 - 1) Do you have thoughts about suicide?
 - 2) If yes, do you have a plan to hurt yourself?

B. PROCEDURES FOR PARTICIPANT DISTRESS

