Health Utility Index/Quality of Life questionnaire (at screening and follow-up visits) – assesses health status and quality of life

Brief Beverage Intake Questionnaire (BEVQ-15) (at screening and follow-up visits) – brief 15-item assessment of types/amounts of beverage intake over the past month

Multifactor Screener (at screening and follow-up visits) – a rapid assessment of approximate intakes of fruits and vegetables, percentage energy from fat, and fiber

Program Evaluation (at 12-month follow-up visit) - includes questions about the participants' perspectives on the helpfulness of various program components and the participants' recommendations for program modifications

Air Force Fitness Test Scores (AF personnel Only) (at the 12-month follow-up visit)

4.0. Human Subject Protection:

4.1. Recruitment:

Participants will be recruited through advertisements at the Base Health and Wellness Center (HAWC) and other locations on Lackland AFB. We plan to use flyers, business cards, posters, newspaper, word-of-mouth, and electronic advertisements in base bulletins. Advertisements will include a phone number and Fit Blue website by which to reach study personnel for more information.

4.2. Consent Processes:

No study specific procedures will be performed without a written and signed informed consent document and HIPAA Authorization. Participants who do not demonstrate the ability to understand or the willingness to sign the written informed consent document will be excluded from study entry.

4.3 Participation Compensation: Subjects will not be paid for participation in this study.

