1. MILD TO MODERATE DISTRESS

- a. If the participant reports mild to moderate stress (but no suicidal thoughts or morbid ideations such as thoughts of wanting to be dead), the participant will be provided a listing of community resources and encouraged to seek help.
- b. Counselor will help the participant develop an action plan to be seen by a mental health professional should their distress persist over multiple sessions or worsen.
- c. Counselor will document the conversation and support materials provided.
- d. Continued distress without professional assistance and support can be a reason to temporarily or permanently withdraw the participant from the *Fit Blue* Weight Loss Intervention protocol.

2. SEVERE DISTRESS AND SUICIDE IDEATIONS WITH NO INTENT OR PLAN Participant reports suicidal thoughts but no intent or plan.

a. Counselor will develop an action plan to get help from a mental health professional. This conversation with the participant and the action plan will be documented.

b. Counselor will follow-up in two business days to ensure that the participant has an appointment with mental health scheduled.

c. Counselor will also inform the participant that if their condition worsens the following emergency resources are available:

1) Mental Health Clinic (open for Walk-Ins during duty hours: [contact])

2) SAMMC ED: [contact]

3) Crisis Hotline call: [name]

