The study aims to enroll 248 participants, 124 participants in each group. This distribution will provide a diverse representation within each intervention group and will provide the necessary information for data and power analysis.

6.3. Statistical Analysis:

The primary data analysis will adhere to the intention-to-treat principle and in the final analysis, the participants will be categorized according to their initial randomization. We will be using the baseline weight as a covariate in the final primary model where we compare the two arms in terms of the percentage of weight loss. We also plan to carry out secondary analyses where we will investigate the efficacy of the intervention in subgroups of Airmen based on gender, race, and years of service in the Armed Forces. We will also evaluate the impact of adherence on outcome, whether it is number of intervention sessions completed, or adherence to dietary intake and physical activity recommendations. Finally, we'll determine the prevalence of Adverse Events and Serious Adverse Events in the two treatment conditions.

6.4 Number of Subjects:

Number of subjects planned for WHASC	Enrolled in full study	248	to result in	248	completing the full study.
TOTAL NUMBER OF SUBJECTS (nation-wide/study-wide):248					

7. Duration of Study: Approximate duration of the study: 54 months

8. Local and External Support Services:

A letter of support from the 559th Medical Group Commander (559 MDG/CC) is attached. The Health and Wellness Center on Lackland AFB will also provide work space for three study staff members as well as for participant visits/follow ups.

9. Intramural (GME) and Extramural Funding Support:

The National Institute of Diabetes and Digestive and Kidney Diseases provided extramural funding for this study.

10. Conflict of Interest:

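### After a critical HUI answer, section 4.9 A.3b words questions on suicidal thoughts and a plan but not on intent, so a denied plan leaves tier 2 and tier 3 unseparated

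*Combined protocol and SAP*

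**What the plan says.** Section 4.9 A names critical answers on three HUI items (33, 35 and 36). If any is given, the counselor finishes the interview and must then "probe briefly for more information about the circumstances of their distress, including potential suicidality". Item A.3b follows. Its lead-in reads "Counselor will ask whether the participant has a plan to harm his/herself (to act on his/her suicidal thoughts", and it words two questions. The first asks whether the participant has thoughts of suicide. The second, put only after a yes, is "If yes, do you have a plan to hurt yourself".

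Section 4.9 B then sets three levels of response, called tiers here:

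- **Tier 1 (B.1)** is mild to moderate distress, "but no suicidal thoughts or morbid ideations such as thoughts of wanting to be dead". The participant gets a list of resources and is encouraged to seek help.
- **Tier 2 (B.2)** is headed "SEVERE DISTRESS AND SUICIDE IDEATIONS WITH NO INTENT OR PLAN", and its one-line definition says the same. The counselor makes an action plan for professional help, names emergency resources in case the condition worsens, and checks within two business days that a mental health appointment has been scheduled.
- **Tier 3 (B.3)** is suicidal thoughts together with either intent or a plan. The participant is not left alone, contact is held until help arrives, and a second staff member calls 911.

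The HUI items are asked before randomization, and "every enrolled participant is asked at each follow-up data collection visit the following distress-related questions". Section 3.6.8 gives the same timing, and sections 3.6.2 and 3.6.5 make that three planned interviews: screening, 4 months and 12 months.

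**The concern.** Tiers 2 and 3 treat intent and plan as two separate facts, and either one is enough for the emergency response. The worded questions collect only one of them. B.3b makes the mismatch visible: its first protective step starts when the participant endorses intent, and no worded question invites that endorsement.

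At stake is the handling of a participant who has suicidal thoughts and means to act but has formed no plan, or denies having one. By the protocol's own definition this person belongs in tier 3. A counselor who asks the two worded questions, hears yes and then no, and goes no further could reasonably turn to tier 2. The response would then be an action plan and a later check on an appointment, instead of continuous contact and a 911 call.

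**Working it through.** The plan gives no figure on this point and no arithmetic applies. The check is to list every outcome of the two worded questions and compare each with the definitions in 4.9 B.2 and B.3.

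| Thoughts (worded) | Plan (worded) | Intent (not worded) | Tier by definition |
|---|---|---|---|
| No | Not asked | – | Neither 2 nor 3 |
| Yes | Yes | Present or absent | 3 |
| Yes | No | Absent | 2 |
| Yes | No | Present | 3 |

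1. If thoughts are denied, tiers 2 and 3 are both ruled out.
2. If thoughts and a plan are both reported, tier 3 applies whatever the intent. Nothing is lost by not asking.
3. If thoughts are reported and a plan is denied, the last two rows give identical answers to the worded questions but fall in different tiers. Intent alone decides between them.

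Next, does any other part of 4.9 supply the missing fact?

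- **The probe in A.3.** It is mandatory and covers potential suicidality. It has no wording and does not name intent, so it may bring intent out but does not ensure it.
- **The lead-in to A.3b.** Its parenthesis speaks of acting on suicidal thoughts, which leans toward intent. It is attached to the plan item, however, and is not part of what the participant is asked.
- **The tier 2 definition.** It makes absence of intent a condition. It tells the counselor what must be true but not to ask about it.

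Each lowers the chance of error in the third case, and none closes it. A single question on intent would separate the last two rows of the table.

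**The case against.** The strongest reply is that the gap appears only when A.3b is read by itself. The protocol never calls A.3b an exhaustive script. The probe is compulsory, and intent falls naturally within suicidality. A counselor who has learned nothing about intent has not met tier 2's stated condition and should not use it. On this reading a sample question is missing, not a safeguard.

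Much of that stands: misplacement is a risk and not a certainty, because a careful counselor will ask. But the text leaves the deciding fact to the counselor's initiative while wording the other two. Section 3.6.1 describes the interventionists as trained in behavior change skills and motivational interviewing. The documents describe no training in suicide-risk assessment, and 4.9 B describes no clinician review of the tier chosen.

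Entry safeguards also count. Exclusion 11 removes unstable psychiatric conditions, and a military provider screens candidates with a record review. These act at entry, and the HUI is repeated at 4 and 12 months.

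Three stronger readings are tempting, and the documents support none of them.

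- A reader might take every planned HUI interview as a measure of exposure. An affected case needs a critical answer, suicidal thoughts, intent, a denied plan and a probe that misses the intent. The documents give no rate for any of these.
- A reader might infer that a misplaced participant goes without help until the two-business-day check. That interval is the time to a check on an appointment. Tier 2 starts an action plan and names walk-in, emergency department and crisis-line resources in the same conversation, and a scheduled counseling call in the counselor-initiated arm may come sooner.
- A reader might infer that a participant who wishes to be dead but denies suicidal thoughts falls outside the safeguard. Read literally, tiers 2 and 3 do not name this state. Tier 1 expressly excludes it, tier 2 is the likely intended place, and the HUI answer that life was not worthwhile is itself critical and triggers the probe. This is a wording gap only.

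**Conclusion.** The point holds in a limited form. The worded questions in 4.9 A.3b do not separate tier 2 from tier 3 when suicidal thoughts are reported and a plan is denied, because intent decides the tier and is not asked. The general probe and tier 2's definition reduce the risk without removing it.

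The frequency is unknown and probably low, given the entry safeguards and the chain of events required. What justifies the change is the gap between the two responses and the small cost of the remedy, not an expected number of cases. Randomization, endpoints, sample size and every efficacy analysis are unaffected.

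The conclusion assumes that the counselor works from 4.9 as written. The attached Data Safety Monitoring Plan is not among the documents reviewed. It may or may not address this, and if it already requires a question on intent, the remaining task is to bring 4.9 into line with it.

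**What to change.** Add one question to 4.9 A.3b, asked whenever suicidal thoughts are reported and whatever the answer on a plan: does the participant intend to act on these thoughts? State that a yes goes to tier 3 with or without a plan, and that tier 2 is used only after both intent and a plan have been asked about and denied.

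Optionally, in the same amendment, have the tier 2 definition name a wish to be dead without suicidal thoughts. This clarifies wording and is not needed for the main fix.

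The cost is one line in the counselor's script, an IRB amendment, under a minute in each interview where suicidal thoughts are reported, and possibly a few more emergency responses. No new staff, visits or instruments are needed.
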